11.3 Planned Analysis

11.3.1 Disposition of Subjects

Number of completed subjects and number of prematurely discontinued subjects breaking down by reason of premature discontinuation including screen-failures will be tabulated.

11.3.2 Data Sets Analyzed

There will be four subject sets defined for this trial: All enrolled subjects set, the Safety Set (SS), the Full Analysis Set (FAS) and the Per-Protocol Set (PPS).

All enrolled Subjects Set will include all subjects having signed their inform consent form. This set will be used for subject disposition summaries and individual listings.

The Safety Set will include all subjects, receiving at least one administration of IMP/AMP, regardless of the quantity. This set will be used for evaluation of safety and description of demographic data and baseline characteristics.

The Full Analysis Set will include all randomized subjects. This set will be used for evaluation of cardiac safety and description of demographic data and baseline characteristics.

The Per Protocol Set will be a subset of the FAS and will include all subjects who have no major protocol deviations throughout their whole trial period. Major deviations will be defined as having an impact on the primary criterion. Primary analysis will be performed on this set.

11.3.3 Protocol deviations

Protocol deviations will be split in major and non-major deviations. A major deviation is defined as a deviation being an impact on the primary criteria. A first categorization will be done in the Statistical Analysis Plan (SAP), then final categorization will be done before the breaking the blind during the Statistical Data Review Meeting.

Frequency and percentages of subjects with protocol deviations will be presented breaking down by status (major/non major).

11.3.4 Demographic and Baseline Characteristics

Demographic parameters are age, sex, race, ethnicity, childbearing potential, body weight, height, and body mass index (BMI). Baseline characteristics are the subject's history (including the medical history), prior contrast agents and concomitant medication, the physical examination and cardiac status from ECG exam at inclusion (QT, QTcF, QTc_{POP}, QTcB and T wave morphology changes and U wave occurrence).

Summary statistics will be calculated for age, body weight, height and BMI and presented overall. Frequency and percentages will be calculated for gender, childbearing potential and ECGs status at inclusion, and presented overall.

Subject's medical history will be coded using the MedDRA dictionary and tabulated by body system, preferred term and status (concomitant or not) and presented overall.

Subject's prior contrast agents and concomitant medication will be coded using the Anatomical Therapeutic Chemical (ATC) Drug dictionary and tabulated by ATC codes and presented overall.

Meal date and start and end time will be listed for each period.

11.3.5 P03277 plasma Concentration and long term elimination

Plasma concentration and long term elimination analysis will be subcontracted to an analytical center and will be supervised by Guerbet.

Specific analytical protocols will be established for analysis of P03277. All parameters description and data will be reported in a separate report. All analytical methods used in this trial will be validated prior to any sample analysis.

- Based on the individual plasma concentration versus time profiles, the plasma concentration will be determined for each subject having received P03277
- Long term P03277 elimination data will be presented in a separate report.

11.3.6 Cardiac safety Data

Cardiac safety data are coming from 12-lead Holter ECG recording read by off-site cardiologists. Triplicate values will be issued for each measurement and the average of the 3 replicates will be used for statistics analyses. Therefore there will be one measure by timepoint by subject.

- **Baseline value**

There will be one baseline by administration period.

The baseline is defined as the mean of 3 triplicates ECGs timepoint measurements within one hour before each IMP/AMP administration.

- **Primary analysis**

Primary analysis will be done using the Per Protocol Set

Primary endpoint is defined as the largest time-matched placebo-corrected, change-from-baseline mean effect of the two P03277 doses of QT interval expressed as QTc according to Fridericia's formula ($\Delta\Delta\text{QTcF}$) (in ms).

The primary analysis is performed using an analysis of covariance (ANCOVA) model for crossover data with baseline data as covariate, sequence, period, time, trial drug, trial drug by time and sex as fixed effect and subject as a random effect.

Test

Differences between means will be tested through the model for each timepoint and for the two doses of P03277 using Student's t-test according to the following items:

- μ_{ij} is the expected average of QTcF for each dose of P03277 at each timepoint (where i is corresponding to one timepoint and j to the 2 doses)
- μ_{ij0} is the expected average of QTcF for corresponding placebo

Null hypothesis

$H_i: \mu_{ij} - \mu_{ij0} \geq 10, i = 1 \dots 9, j=1,2$

Alternative hypothesis

$K_i: \mu_i - \mu_{i0} < 10, i = 1 \dots 9, j=1,2$

For each timepoint, the two-sided 90% confidence intervals of the difference between each of the two doses of P03277 and placebo is calculated for testing above hypotheses.

The trial will be considered as successful if, no test is significant that is to say if the upper range of the 90% CI is lower than 10 ms for all tests.

The appropriateness of a linear model will be assured by inspecting the goodness of fit, e.g., by looking at normal QQ-plots for the residuals and plots of the residuals over predicted values. If there is an indication that a linear model is inappropriate, the nonlinearity detected will be taken into account by an appropriate transformation of the concentration values (e.g., $\log(\text{conc}/\text{lloq})$) or by the use of an appropriate nonlinear model.

- **Secondary analysis:**

Secondary analysis will be done using the Full Analysis Set except otherwise specified.

- Primary analysis will be repeated using the Full Analysis Set.
- Assay sensitivity analysis:

The assay sensitivity analysis is performed using an analysis of covariance (ANCOVA) model for crossover data with baseline data as covariate, time, trial drug, trial drug by time and sex as fixed effect and subject as a random effect.

Test

Differences between means will be tested through the model for each timepoint using Student's t-test according to the following items:

- μ_i is the expected average of QTcF for positive control at each timepoint (where i is corresponding to one timepoint)
- μ_{i0} is the expected average of QTcF for corresponding placebo

Null hypothesis

$H_i: \mu_i - \mu_{i0} \leq 0, i = 1 \dots 5$

Alternative hypothesis

$K_i: \mu_i - \mu_{i0} > 0, i = 1 \dots 5$

For each timepoint, the p-value for comparing the doses of positive control with corresponding placebo is calculated for testing above hypotheses.

Hochberg's step-up procedure:

Let p_1, p_2, p_3, p_4, p_5 be the ordered p-values (from the lower to the upper value) and H_1, H_2, H_3, H_4, H_5 be the corresponding ordered null hypothesis. The testing procedure starts with the less significant comparison and continues as long as tests are not significant (meaning that the alternative statistics is not met). The procedure stops the first time a significant comparison occurs and all remaining hypotheses will be not tested.

In the first step, H_5 is rejected if $p_5 \leq \alpha$, in the second step (if any) H_4 is rejected if $p_4 \leq \alpha/2$, in the third step (if any), H_3 is rejected if $p_3 \leq \alpha/3$, in the fourth step, H_2 is rejected if $p_2 \leq \alpha/4$, and in the fifth and last step, H_1 is rejected if $p_1 \leq \alpha/5$ with α being the 1-sided significance level of 0.025.

The trial will be considered as positive in terms of assay sensitivity if, at the end of the Hochberg's step-up procedure, at least one test is significant.

- Assay sensitivity will be repeated using the Per Protocol Set.
- Same analysis as for primary end-point will be repeated for QT, QTc_{POP} and QTcB
- Descriptive statistics at any time from administration up to 24h post dose of Time-matched change from baseline, placebo controlled, of the QT, QTcF, QTc_{POP} and the QTcB will be provided.
- Number and percentage of subjects showing values above predefined threshold for QT, QTcB and QTcF (under placebo and two doses of P03277):
 - Absolute QTc interval prolongation:
 - QTc interval > 450 ms
 - QTc interval > 480 ms
 - QTc interval > 500 ms
 - Change from baseline in QTc interval:

- QTc interval increases from baseline > 30 ms
 - QTc interval increases from baseline > 60 ms
- Descriptive statistics at any time of QT, QTcF, QTc_{POP}, QTcB, RR (ms), QRS (ms), PR (ms), Heart rate (bpm)
- QT/QTc values according to plasma concentrations of P03277.
- Descriptive statistics on T wave morphology changes, U wave occurrence and sinus rhythm will be presented:
- Descriptive statistics on bradycardia and arrhythmia will be presented

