The null hypothesis is that the difference between each of the two doses of P03277 and placebo for the largest mean change from baseline for the QTcF is greater than the non-inferiority margin set to 10 ms according to regulatory guidance. This test is performed at a one-sided at the 5% significance level, which is equivalent to compare the upper limit of the two-sided 90% confidence intervals of the difference with the non-inferiority margin of 10 ms. To conclude that P03277 is non-inferior to placebo, the null hypothesis has to be rejected for both doses simultaneously.

The primary analysis is performed using an analysis of covariance (ANCOVA) model for crossover data with the baseline data and sex as covariate.

- Secondary analyses:

[figure not shown]
[figure not shown]

[figure not shown]

- In order to validate the assay sensitivity, the trial must show that the positive control increases the QTcF by at least 5 ms.

The null hypothesis is that the difference between the positive control and placebo for mean change from baseline for the QTcF is less than 5 ms according to regulatory guidance. This test is performed one-sided at the 5% significance level. To conclude that positive control is superior to placebo, the null hypothesis has to be rejected.

As multiple timepoints are examined separately, the overall Type I error rate needs to be adjusted. To address this issue, the method described by Hochberg and Tamhane will be used. To minimize the correction and because the positive control effect is well known, only five timepoint around the peak effect (1h, 1h30, 2h, 3h and 4h) will be used.

- Same analysis as for primary end-point will be repeated for QT, QT_{cPOP} and QTcB
- Descriptive statistics at any time from administration up to 24h post dose of Time-matched change from baseline, placebo controlled, of the QT, QTcF, QT_{cPOP} and the QTcB will be provided
- Number and percentage of subjects showing values above predefined threshold for QT, QTcB and QTcF (under placebo and two doses of P03277)
- Descriptive statistics at any time of QT, QTcF, QT_{cPOP}, QTcB, RR (ms), QRS (ms), PR (ms), Heart rate (bpm)
- QT/QTc values according to plasma concentrations of P03277
- Descriptive statistics on T wave morphology changes, U wave occurrence and sinus rhythm will be presented
- Descriptive statistics on bradycardia and arrhythmia will be presented
- Descriptive statistics will summarize safety data:
 - Biochemistry and hematology

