11 STATISTICAL ANALYSIS

The following section summarizes the statistical analysis method, which is fully described in the Statistical Analysis Plan.

Continuous variables (e.g., age) will be summarized using the number of observations (n), mean, standard deviation (SD), median, minimum, and maximum.

Categorical variables (e.g., sex, race and ethnicity) will be summarized using the number of observations (n) and percentage in each category.

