11.1 Statistical Method (null and alternative hypotheses)

Primary analysis

Primary endpoint is defined as the largest time-matched placebo-corrected, change-from-baseline mean effect of the two P03277 doses of QT interval expressed as QTc according to Fridericia's formula ($\Delta\Delta\text{QTcF}$) (in ms).

Primary endpoint is considered as following a standard normal distribution. Normality will be checked by means of plots.

Per ICH E14, a "negative" (successful) 'thorough QT/QTc trial' is one in which the upper bound of the 95% one-sided confidence interval for the largest time-matched placebo-corrected, change-from-baseline mean effect of the drug on the QTc interval excludes 10 ms. Consequently, the trial must show that both 0.1 and 0.3 mmol/kg doses of P03277 do not increase the QT interval corrected by Fridericia formula (QTcF) at all timepoints.

The null hypothesis is that the difference between each of the two doses of P03277 and placebo for the largest mean change from baseline for the QTcF is greater than the non-inferiority margin set to 10 ms according to regulatory guidance. An Intersection-Union test is performed at a one-sided 5% significance level. This is equivalent to compare at each timepoint the upper limit of the two-sided 90% confidence intervals of the difference between each of the two doses of P03277 and placebo with the non-inferiority margin of 10 ms. To conclude that P03277 is non-inferior to placebo, the null hypothesis has to be rejected for all timepoints and both doses simultaneously hence the overall Type I error rate does not need to be adjusted.

Assay sensitivity

Assay sensitivity assessment is defined as the largest time-matched placebo-corrected, change-from-baseline mean effect of moxifloxacin of QT interval expressed as QTc according to Fridericia's formula ($\Delta\Delta\text{QTcF}$)(in ms).

In order to validate the assay sensitivity of the trial, the trial must show that the positive control increase the QTcF by at least 5 ms for at least one timepoint.

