The null hypothesis is that the difference between the positive control and placebo for the mean change from baseline for the QTcF is less than 5 ms according to regulatory guidance. This test is performed one-sided at the 5% significance level which is equivalent to compare the upper limit of the two-sided 90% confidence intervals of the difference with 5 ms. To conclude that positive control is superior to placebo, the null hypothesis has to be rejected at, at least, one timepoint.

As multiple timepoints are examined separately, the overall Type I error rate needs to be adjusted. To address this issue, the method described by Hochberg and Tamhane will be used. To minimize the correction and because the positive control effect is well known, only five timepoint around the peak effect (1h, 1h30, 2h, 3h and 4h) will be used.

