11.2 Sample Size

A total of 48 subjects will be included in the study trial.

The sample size is determined using published recommendations for a thorough QT trial (Statistical Issues Including Design and Sample Size Calculation in Thorough QT/QTc Studies [4]).

N can be estimated by $N = 2 * (t_{\alpha}(\gamma) + t_{\beta}(\gamma))^2 [\sigma / (\delta - 10)]^2$

where

- σ^2 is the within subject variability
- $\gamma = N - 2$
- $\beta' = 1 - (1 - \beta)^{1/L}$ where β is the Type II error and L the number of measurements
- α is the Type I error
- $t_{\alpha}(\gamma)$ the critical values for a Student T distribution with γ degrees of freedom at an α level.
- δ is the expected difference between active drug and placebo (0 if no difference expected, >0 if drug is expected to slightly increase QT)

Considering an expected intra-variability of the primary endpoint of $\sigma = 9$ ms and an expected difference of $\delta = 2$ ms between P03277 (two doses) and placebo, 40 subjects are needed to demonstrate non-inferiority with a non-inferiority margin of 10 ms, a power of $1 - \beta = 85\%$ and a Type I error of $\alpha = 5\%$ one-sided on the $L = 9$ measurements.

This sample size is also sufficient to detect a difference of 5 ms (with an expected difference of 12 ms for at least one timepoint and an expected intra-variability of the primary endpoint of $\sigma = 9$ ms) of the primary endpoint between moxifloxacin and placebo with a power of 85%.

To account for potential dropouts and/or unevaluable data points, 48 subjects will be randomized in the trial. The recruitment could be stopped before 48 subjects from the time the number of fully evaluable subjects for the primary criterion is 40. That is to say having took part to the study, till the last scheduled ECG Holter recording.

A dropout is a subject who is prematurely discontinuing the trial before the end of the last Holter ECG recording.

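### Protocol 11.3.6 tests assay sensitivity against 0 ms at one-sided 0.025, while the rest of the protocol and the SAP set 5 ms at one-sided 0.05

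*Protocol*

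**What the plan says.** **Protocol 11.3.6**, assay sensitivity analysis, gives the null as "\mu_i - \mu_{i0} \leq 0, i = 1 \dots 5", with the alternative above 0. Hochberg's step-up procedure runs over 1, 1.5, 2, 3 and 4 h, with alpha "being the 1-sided significance level of 0.025". The model has "baseline data as covariate, time, trial drug, trial drug by time and sex as fixed effect and subject as a random effect"; sequence and period are absent.

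**Protocol synopsis and 11.1** set a different standard. The synopsis says that "the trial must show that the positive control increases the QTcF by at least 5 ms". Section 11.1 says that "the trial must show that the positive control increase the QTcF by at least 5 ms for at least one timepoint", with a null of less than 5 ms tested one-sided at 5%. It calls this test "equivalent to compare the upper limit of the two-sided 90% confidence intervals of the difference with 5 ms".

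**Protocol 11.2** bases the moxifloxacin power of 85% on a 5 ms threshold, an expected 12 ms at one or more timepoints, and a within-subject SD of 9 ms.

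**The SAP** sets all tests at 5% one-sided (3.1), compares the lower limit of the 90% interval with 5 ms (3.2), and runs Hochberg at one-sided 0.05 (5.5.2). Its assay model includes sequence and period.

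**Precedence.** Protocol section 11 states that it "summarizes the statistical analysis method, which is fully described in the Statistical Analysis Plan". The SAP is dated 24 July 2018 and is based on protocol version 4.0. The current protocol is version 5.0, dated 31 August 2018.

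**The concern.** Protocol 11.4.5 and SAP 3.8 both make the moxifloxacin result a condition of success: the trial succeeds only if both P03277 doses pass and moxifloxacin's null is rejected at one or more timepoints. Under a 0 ms null, a moxifloxacin effect no greater than 5 ms can validate the assay, so the trial could be called sensitive without showing what the synopsis and 11.1 require.

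Three lesser points sit beside this.

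- Section 11.1 names the upper limit of the interval. Rejecting a null of less than 5 ms needs the lower limit, as SAP 3.2 has it.
- The assay models in 11.3.6 and SAP 5.5.2 differ in sequence and period. SAP Section 4 records that time is dropped from the model, but is silent on these two terms, the margin and the alpha.
- SAP 5.5.2 does not say how the p-value against 5 ms is obtained. The ESTIMATE statement shown returns a two-sided p-value against 0.

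**Working it through.** **Inputs.** Protocol 11.2: SD 9 ms, 40 evaluable subjects (48 randomized), expected moxifloxacin effect 12 ms, threshold 5 ms, and df = N − 2 from its formula. Protocol 11.1 and 11.3.6: five timepoints, so the last Hochberg step uses alpha/5. The correlation between timepoints is not given; 0.3, 0.5 and 0.7 are assumed.

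**1. Reproduce the stated 85%.** SE = 9 × √(2/40) = 2.01 ms. Power for a true 12 ms at one timepoint, at alpha/5 (noncentral t):

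| Null | Alpha/5 | N = 40 | N = 48 |
|---|---|---|---|
| 5 ms | 0.05/5 = 0.01 | 84.8% | 91.5% |
| 5 ms | 0.025/5 = 0.005 | 77.3% | 86.3% |
| 0 ms | 0.025/5 = 0.005 | 99.9% | over 99.9% |

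The protocol's own t formula gives 85.0% for the first row at N = 40. Section 11.2 therefore describes the 5 ms test. The 0 ms test of 11.3.6 would give 99.9%.

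**2. Observed effect needed at the last Hochberg step** = margin + t(1 − alpha/5, N − 2) × SE.

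- 11.3.6, N = 40: 0 + 5.46 = 5.46 ms
- SAP rule, N = 40: 5 + 4.89 = 9.89 ms
- At N = 48: 4.94 ms and 9.43 ms

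**3. Chance of declaring assay sensitivity when the true peak is 5 ms.** Simulation of 100,000 trials per case: N = 40, paired differences with SD 9√2 ms, equal correlation between timepoints, t tests with 39 df, full Hochberg step-up. Ranges are over correlations 0.3–0.7.

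| True effect over the five timepoints | 11.3.6 (0 ms, 0.025) | SAP (5 ms, 0.05) | Two-sided p against 0, Hochberg at 0.05 |
|---|---|---|---|
| 5 ms at one, 0 elsewhere | 42–43% | 0.9–1.0% | 44% |
| 3, 4, 5, 4, 3 ms | 53–66% | 1.4–1.5% | 53–66% |
| 5 ms at all five | 70–85% | 3.3–4.5% | 70–85% |

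The last column shows what happens if the printed ESTIMATE p-values go straight into Hochberg: the weaker rule returns through the program.

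**4. Full Hochberg power.** With 12 ms at one timepoint and 5 ms at the others, the 5 ms rule has power 85% at alpha 0.05 and 78% at alpha 0.025. The SAP rule thus keeps the planned power.

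**5. Unadjusted 90% limits.** With a true 5 ms at all five timepoints, an unadjusted lower limit above 5 ms at any one of them occurs in 14–19% of trials. That is not equivalent to the Hochberg rule.

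**The case against.** The strongest reply is that the matter is already settled. Protocol section 11 defers to the SAP, the SAP text is coherent, and protocol 11.1, which is the section on hypotheses, agrees with it. Section 11.3.6 is the outlier. This stands, and it limits the practical risk. It does not remove the contradiction: the protocol is the later document and still prints the other rule as its planned analysis.

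Other points that stand in part:

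- Section 11.2 gives no alpha for moxifloxacin, so 0.05/5 is inferred. If the sample size meant there were 48, a 5 ms null with 0.025/5 would give 86.3%. The power figure therefore excludes the 0 ms null but does not settle alpha by itself. Section 11.1 and the SAP settle it.
- Protocol 4.0 is not available, so it is unknown whether SAP Section 4 failed to declare a change or the protocol text moved afterwards.
- SAP 5.5.2 ties the p-values to its stated hypotheses, so using p-values against 0 would breach the SAP. The ESTIMATE issue is a gap in specification, not an adopted rule. Likewise, neither document adopts unadjusted limits as its final rule.
- The SAP fits four treatments in one model, so residual df would be nearer 113 with complete data at N = 40. The observed effects needed become 5.27 and 9.75 ms. The gap barely changes.
- No effect of omitting sequence and period has been estimated. That is an alignment point only.

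**Conclusion.** The concern holds and should be fixed. Protocol 11.3.6 states a margin and an alpha that contradict the synopsis, 11.1 and the SAP, and its margin also contradicts the basis of the 85% power. On balance it is much the weaker test: the observed effect needed at the last step is about 4.4 ms lower (9.89 − 5.46), and a true 5 ms at all five timepoints passes in 70–85% of trials instead of 3.3–4.5%.

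These figures rest on N = 40, an SD of 9 ms and assumed correlations of 0.3–0.7. Widening the correlation to 0–0.9 (normal approximation) gives 64–96% against 2.7–5.0%, so the direction does not depend on that choice. The severity is held down by the protocol's deference to a SAP whose written rule is sound.

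**What to change.** **Lower-cost route.** Add one entry to SAP Section 4 saying that SAP 3.2 and 5.5.2 replace the margin, alpha and model of protocol 11.3.6 for assay sensitivity. Update the SAP's protocol reference to version 5.0 and list any other remaining differences.

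**In SAP 5.5.2, on either route,** state the decision rule once: Hochberg at one-sided 0.05 on the five one-sided p-values from t = (estimate − 5)/SE at 1, 1.5, 2, 3 and 4 h. Say that the printed ESTIMATE p-value is not used. It would also help to say that any adjusted lower limit is descriptive, and that an unadjusted 90% limit above 5 ms at a single timepoint is not the rule.

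**Full route.** In protocol 11.3.6, change the hypotheses to a difference of at most 5 ms against more than 5 ms, set alpha to one-sided 0.05, and align the model terms with SAP 5.5.2. In 11.1, change the upper limit to the lower limit.

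**Cost.** The lower-cost route takes one SAP entry and a few sentences. The full route adds a protocol amendment, with the ethics committee and competent authority submission that protocol 13.2 requires. Neither needs new data or subjects. Either should be in place before unblinding, so that the success rule cannot appear to have been chosen after the results.
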